5.4 SUBJECT RETENTION

Although the registry sample size has been calculated with a 10% subject attrition rate per year (41% total in 5 years), subject retention in a 5 year registry may pose additional, unforeseen challenges. BIOTRONIK will provide additional tools to the sites in an effort to minimize the number of subjects that are lost to follow-up. The EDC system includes an overview of each subject's follow-up schedule, including the windows for each follow-up. The EDC system also provides a subject follow-up scheduling tool in the form of a Visit Scheduler Report. This report allows research personnel to become alerted to and track all registry subjects that should be scheduled for upcoming follow-ups. Monitoring visits include a review of subjects that may be lost to follow-up (see Section 7).

5.5 SUBJECT DATA CONFIDENTIALITY

All information sent to BIOTRONIK pertaining to each subject will be kept confidential at BIOTRONIK and is subject to FDA audit. Source documents used to support endpoint adjudication by the CEC in the Protego DF4 registry will have all confidential subject identifiers redacted prior to transmission. Reports submitted to the physician or publications of registry results will not make any reference to subject names.

In order to verify the registry data and ensure registry integrity, monitors from BIOTRONIK, the FDA, and the reviewing Institutional Review Board (IRB) may review and/or copy the registry records.

6. RISKS AND RISK MINIMALIZATION

All devices included in this registry are legally marketed and being prescribed by physicians according to FDA approved indications for use.

As with any implantable device, there are always potential risks that accompany the device. The following list provides the potential risks that may occur with the Protego DF4 lead in combination with an ICD or CRT-D device.

- Acceleration of arrhythmias
- Air embolism
- Allergic reactions to contrast media
- Arrhythmias
- Bleeding
- Body rejection phenomena
- Cardiac tamponade
- Chronic nerve damage
- Damage to heart valves
- Damage to lead during implant procedure
- Device migration
- Elevated pacing thresholds
- Embolism
- Erosion or pocket erosion
- Extrusion
- Fluid accumulation
- Hematomas, cysts, or fibrotic tissue
- Incomplete lead connection with the pulse generator
- Infection
- Inappropriate detection of ventricular arrhythmias
- Inappropriate therapy, including inappropriate shocks
- Keloid formation
- Lead abrasion and discontinuity
- Lead migration / dislodgment
- Lead fracture / insulation damage
- Lead perforation
- Lead-related thrombosis

-
- Local tissue reaction / fibrotic tissue formation
 - Muscle or nerve stimulation
 - Myocardial damage
 - Myopotential sensing
 - Pacemaker mediated tachycardia
 - Pneumothorax
 - Potential death due to inability to defibrillate or pace
 - Psychological effects (dependency, depression, fear of premature battery depletion, fear of shocking while awake, fear that shocking ability may be lost, anxiety about device resulting from frequent shocks, imagined (phantom) shock)
 - Random component failure
 - Shunting current or insulating myocardium during defibrillation with internal or external paddles
 - Thromboembolism
 - Undersensing of intrinsic signals
 - Valvular damage
 - Venous occlusion
 - Venous or cardiac perforation
 - Ventricular ectopy

These risks can be minimized through use of strict aseptic technique, compliance with the registry protocol and technical implant procedures, adherence to the guidelines for selection of subjects, close monitoring of the subject's physiologic status during the implant and follow-up procedures, and by promptly supplying BIOTRONIK with all pertinent information required by this protocol.

BIOTRONIK foresees no additional risks associated with this registry beyond those stated in the labeling for the respective pulse generators and leads.

7. REGISTRY MONITORING

7.1 SUMMARY

BIOTRONIK's responsibility as the clinical registry sponsor is to ensure protocol and regulatory compliance through proper monitoring of the investigation. BIOTRONIK requires IRB/EC review and a subject Informed Consent Form for all after-market research. Monitoring may be conducted on-site at the investigational site or remotely by BIOTRONIK monitors.

Through on-site or centralized monitoring, BIOTRONIK will assess the site's performance in the following areas:

- Verification that informed consent was obtained and documented properly
- Adherence to protocol eligibility criteria and requirements
- Conduct and documentation of procedures and assessments related to:
 - o Study endpoints
 - o Protocol required safety assessments
 - o Evaluating, documenting, and reporting unanticipated adverse device effects, subject deaths, and withdrawals, especially when a withdrawal may be related to an adverse event.
- Investigator oversight and delegation of authority to study personnel
- Verification of study-specific required documentation
- Conduct and documentation of procedures essential to trial integrity
- Adherence to the applicable FDA regulations regarding the obligations of the investigator and maintenance of records.

As the investigator, the physician is responsible for conducting the registry in accordance with the signed agreement, the investigational plan (protocol), applicable laws, FDA regulations, and any conditions of approval imposed by the reviewing IRB/EC. The principal investigator must also accept responsibility for all aspects of the registry including the actions of any sub-investigators participating in the registry at the investigational site.

7.3 MONITORING VISITS

A monitor will conduct monitoring visits at investigational sites in accordance with the Monitoring Plan. Sites are required to support these visits and the study monitoring effort. On-site monitoring visits will also provide an assessment of the continued acceptability of the facilities to continue participation in the registry.

7.4 CENTRALIZED MONITORING

Centralized monitoring will be conducted throughout the course of the study in accordance with the Monitoring Plan. Some examples of data that may be monitored remotely include device data and adverse events reported in the EDC system. Sites are required to support centralized monitoring by providing source documents to BIOTRONIK in order to source data verify data reported in the EDC system and resolving queries in a timely manner.

8. REGISTRY COMPLETION

BIOTRONIK will notify the post-approval registry site upon completion or termination of the registry or investigator's participation in the registry. At BIOTRONIK's request, an investigator will return any study specific equipment and pertinent information in their possession. BIOTRONIK will provide a final report to each investigational site as required by FDA regulations. After FDA has granted approval to terminate this post-approval registry, BIOTRONIK personnel may conduct a registry closure visit according to the monitoring plan. During this visit, BIOTRONIK will verify registry records and ensure that the investigator understands any applicable regulatory requirements including those related to record retention. The investigator must retain records related to the registry for a period of 2 years after the registry is completed.

In the event that the registry is suspended or terminated, the investigator must inform all enrolled subjects who at that time have not yet completed the registry. Standard patient care will be ensured by the registry site.

9. PROTOCOL COMPLIANCE

The investigator is responsible for conducting the registry in accordance with the signed agreement, the investigational plan (protocol), applicable laws, FDA regulations, and any conditions of approval imposed by the reviewing IRB/EC. The investigator shall notify BIOTRONIK and the reviewing IRB/EC in writing no later than 5 working days after any significant deviation from the investigational plan to protect the life or physical well-being of a subject in an emergency. Except in such emergency, prior approval by BIOTRONIK is required for significant deviations from the investigational plan.

BIOTRONIK categorizes protocol noncompliance instances as either violations or deviations. Both protocol violations and deviations will be reported to FDA during interim reports.

9.1 PROTOCOL VIOLATIONS

Protocol violations are defined as instances where the protocol requirements and/or regulatory guidelines were not followed, and are generally more serious in nature. Protocol violations are considered to potentially affect the scientific soundness of the plan and/or the rights, safety, or welfare of subjects. Protocol violations include, but are not limited to:

- Failure to obtain consent
- Subject inclusion/exclusion violations and protocol requirement violations that affect the primary endpoints of the registry design

These violations will be reported to FDA in accordance with applicable regulatory timelines and the site must notify the reviewing IRB/EC per the IRB/EC's reporting requirements. The site should provide a copy of the IRB/EC protocol noncompliance notification (as applicable) to BIOTRONIK. Protocol violations must also be reported to BIOTRONIK via Protocol Noncompliance eCRFs.

9.2 PROTOCOL DEVIATIONS

Protocol deviations are deviations from the requirements of the protocol in such a manner whereby data is unusable or not available. Protocol deviations are less serious in nature and do not require IRB/EC notification as long as they do not have an effect on the rights, safety, or welfare of the registry subject. Protocol deviations include, but are not limited to:

- Procedure not performed within the allowed follow-up window
- Required data not obtained

The site must report protocol deviations to BIOTRONIK via Protocol Noncompliance eCRFs. Both protocol deviations and violations will be reported to FDA in progress reports.

10. ADVERSE EVENTS

An adverse event (AE) is defined as any unfavorable and unintended event that occurs during the course of the study. The investigator will be required to assess and classify each reported adverse event as related to either the implant procedure, implanted pulse generator, Protego lead, right atrial lead, left ventricular lead, or as non-procedure non-system related. For subjects enrolled prior to implant, only adverse events from the first implant attempt onward will be collected.

The investigational site should report each adverse event via an Adverse Event eCRF and provide a copy of the IRB/EC adverse event notification to BIOTRONIK.

10.1 REPORTABLE ADVERSE EVENTS

The following AEs (sorted by classification) will be reported. The classifications listed below are general classifications for site reporting purposes. Detailed information for many classifications is located in Appendix A. The CEC charter may include alternate classifications for some adverse events.

10.1.1 Implant Procedure-Related Adverse Events

An AE will be classified as procedure-related if any one of the following occurred as a result of the implant procedure:

- Arrhythmias associated with the implantation of the lead
- Cardiac perforation with or without tamponade
- Coronary sinus dissection
- Damage to lead during procedure (e.g. accidental cut to lead body during pocket revision, device replacement, etc.)
- Hematoma
- Primary infection
- Lead dislodgement during a procedure (e.g. during pocket revision, device replacement, etc.)
- Lead reversed in header
- Loose set-screw
- Non-healing pocket dehiscence requiring intervention
- Pneumothorax
- Pocket pain
- Pulmonary embolism
- Venous occlusion

10.1.2 Pulse Generator-Related Adverse Events

An AE will be classified as pulse generator-related if any one of the following occurred:

- DF4 header connector malfunction
- DF4 header fluid intrusion
- Device migration
- Premature battery depletion
- Pulse generator failure
- Skin erosion

10.1.3 Lead-Related Adverse Events

An AE will be classified as lead-related if any one of the following occurred:

- Cardiac perforation
- Diaphragmatic/extracardiac stimulation
- High pacing threshold³
- Intermittent capture / no lead capture
- Lead conductor fracture
- Lead dislodgement
- Lead impedance out of range, high impedance⁴
- Lead impedance out of range, low impedance⁴
- Lead failure
- Lead oversensing not due to external noise
- Lead oversensing due to external noise
- Lead-related thrombosis
- Lead-related infection
- Lead undersensing or loss of sensing
- Other unexpected complications that are identified through imaging and considered related to the ICD lead or DF4 connector

³ High pacing threshold is defined as:

A. At implant, threshold that is greater than 3.0V at 0.4ms or 0.5ms, OR

B. At follow-up, threshold that has increased two fold from the chronic (3 month follow-up) threshold value and is greater than 3.5V at 0.4ms or 0.5ms.

⁴ Lead impedance out of range is defined as a pacing impedance measurement of ≤ 200 Ohms or ≥ 2000 Ohms or a shock impedance measurement of ≤ 20 Ohms or ≥ 150 Ohms.

For each of these lead-related AEs, indicate:

- Confirmed lead integrity failure
- Suspected lead integrity failure
- No lead integrity failure

10.1.4 Non-Procedure Non-System Related Adverse Events

An AE will be classified as non-procedure non-system related if any of the following occur and require a system revision or explant:

- Twiddler's syndrome
- Secondary infection
- Ablation sequelae

10.2 ENDPOINT ANALYSIS

All protocol defined adverse events included in the primary and secondary endpoint analysis will be adjudicated by the Clinical Events Committee (CEC) (see Section 2.1). The CEC will have the responsibility to adjudicate the classification and category of each reported adverse event as implant procedure, implanted pulse generator, lead, or non-procedure non-system related. For each adverse event, the CEC will indicate whether the adverse event relatedness to the Protego lead is: not related, related, possibly related, or unknown.

In evaluation of the two primary endpoints for the post-approval registry, the estimates of AE rates will be based on the number of subjects with at least one "related" AE as a proportion of total subjects. Subjects with a final adjudicated related AE classification of "possibly related", "not related" or "unknown" will not have that individual event contribute to or be included in the evaluation of primary safety endpoints. The same rules will be used for purposes of Kaplan-Meier survival analyses, described in Section 2.4.2.

Secondary endpoint 3, which includes AEs that were excluded from primary safety endpoint 1 through 5 years post-implant, will also be summarized as AE rates along with their associated, exact 95% confidence intervals.

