2.3 SAMPLE SIZE ANALYSIS

The estimated sample sizes required to evaluate primary endpoints 1 and 2 are based on a superiority comparison of the overall Protego DF4 lead AE free-rate to 92.5% at 5 years, and a non-powered, superiority comparison for those individual lead-related AEs to 1% at 5 years. The sample size for primary safety endpoint 1 was calculated based on the following assumptions:

Assumptions for primary safety endpoint 1

- Study Design: nonrandomized registry
- Test basis: exact binomial test
- Type I error (alpha): 0.025 (one-sided for superiority)
- Statistical power: 80%
- Estimated AE-Free Rate at 5 years: 95.0% for Protego Leads
- Performance goal for AE-Free Rate at 5 years: 92.5%

For primary safety endpoint 1, a total of 750 evaluable Protego leads would be required to demonstrate superiority to an AE free-rate of 92.5% (see Table 3). Assuming a 10% loss to follow-up rate per year over 5 years of follow-up (average of 8.2% of original population per year), a total of 1271 ($=750/0.9^5$) subjects with an ICD lead would be required to be enrolled to evaluate primary safety endpoint 1.

Assumptions for primary safety endpoint 2

- Estimated individual AE rate at 5 years: 0.4%
- Allowable two-sided, upper 95% confidence bound: 1%

For primary safety endpoint 2, a total of 1000 evaluable subjects with Protego DF4 leads would be required to demonstrate a two-sided, upper 95% confidence bound of 1%, assuming an expected individual AE rate of 0.4% (see Table 3). Assuming a 10% loss to follow-up rate per year over 5 years of follow-up (average of 8.2% of original population per year), a total of 1694 ($=1000/0.9^5$) subjects would be required for evaluation of primary safety endpoint 2.

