2.3.1 Attrition

For the sample size calculation, a maximum loss to follow-up of 10% per year (41% over 5 years) was assumed. The loss to follow-up rate encompasses all causes for subjects to be exited from the registry, including death, device explants, subject directed withdrawals, physician-directed withdrawals, and loss of contact with the subject.

Table 3: Primary Safety Endpoints Sample Sizes

	Primary Safety Endpoint 1	Primary Safety Endpoint 2
Sample Size of Evaluable Subjects	750 subjects	1000 subjects
Total Adjusted for Attrition	1271 subjects	1694 subjects

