2.4 DATA ANALYSES

The analysis population for all primary endpoints in the registry will be the intention-to-treat (ITT) population. This population analysis will include all subjects who provide informed consent, met the enrollment criteria, and in whom a Protego lead was successfully implanted. Subjects enrolled prior to the Protego lead implant but not successfully implanted due to a Protego lead related complication (such as cardiac perforation caused by the Protego lead) will also be included in the ITT population.

Descriptive statistics will be used to present and summarize the data collected in the clinical registry. Frequency distributions and cross tabulations will be presented for discrete variables. Means, standard errors, and ranges will be presented for continuous variables.

Confidence intervals for the AE free-rate will also be estimated based on Kaplan-Meier estimates for freedom from adverse events together with the associated standard errors.

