2.4.3 Missing Data

All possible steps will be taken to minimize missing data in the registry. This includes but is not limited to monitoring of registry forms for completeness and supporting efforts to track and maintain contact with registry subjects during the follow-up period.

The reasons for any missing data in the registry will be documented. BIOTRONIK will examine both missing-data patterns, which describe which values are observed and which are missing, and the missing-data mechanisms, which concerns the relationship between missingness and the values of variables in the registry data set².

For evaluation of the long-term primary registry endpoints (safety endpoints 1 and 2), only subjects who achieve 5 years of follow-up or have experienced an adverse event prior to 5 years will be included in the final evaluation of the associated hypotheses. The secondary endpoint of other AEs at 5 years, excluded from the primary safety analyses, will be analyzed in similar manner. There will be no imputation for these missing adverse event outcomes.

For purposes of Kaplan-Meier survival analyses, described in Section 2.4.2, all AE data on enrolled subjects will be included with follow-up times censored at the time of withdrawal or last completed follow-up visit representing the time of the last known AE status.

² R.J.A. Little and D.B. Rubin, 2002, *Statistical Analysis with Missing Data*, 2nd edition, Wiley and Sons

Secondary endpoints, which include successful sensing and pacing, pacing thresholds, sensing and impedance measurements will be analyzed in two ways. First, all available results will be summarized by scheduled visit through the 5 years of registry follow-up. Secondly, a last value carried forward (LVCF) will be used to estimate the values at the final 5-year follow-up evaluation for subjects who withdraw prior to 5 years.

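### The primary tests have two conflicting denominators (Sections 2.4/10.2 against 2.4.3), and under the planned attrition one can favour the device while the other penalises it

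*Combined protocol and SAP*

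**What the plan says.** - **Section 2.4 (Data Analyses):** "The analysis population for all primary endpoints in the registry will be the intention-to-treat (ITT) population". It is defined so: "This population analysis will include all subjects who provide informed consent, met the enrollment criteria, and in whom a Protego lead was successfully implanted". Subjects whose implant failed because of a lead complication are added.
- **Section 10.2 (Endpoint Analysis):** for both primary endpoints, the rate is the number of subjects with at least one related "AE as a proportion of total subjects". Total subjects is not defined.
- **Section 2.4.3 (Missing Data):** for the final tests of endpoints 1 and 2, "only subjects who achieve 5 years of follow-up or have experienced an adverse event prior to 5 years will be included". It adds: "There will be no imputation for these missing adverse event outcomes".
- **Section 2.3 (Sample Size Analysis):** "Test basis: exact binomial test"; "Type I error (alpha): 0.025 (one-sided for superiority"); 80% power; 95.0% expected against a goal of 92.5%. The 750 and 1000 evaluable subjects are divided by 0.9^5 to give 1271 and 1694.
- **Section 2.3.1 (Attrition):** "a maximum loss to follow-up of 10% per year (41% over 5 years) was assumed", covering all causes of exit, including death, explant and withdrawal.
- **Kaplan-Meier:** planned for additional confidence intervals (2.4) and trend monitoring (2.4.2), with censoring at withdrawal or last completed visit (2.4.3). It is not the primary test; Section 2.4.1 specifies the exact binomial test and exact intervals.

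**The concern.** The denominators differ in one group only: subjects who leave before 5 years without a counted AE. The plan allows for this group to be about two fifths of the registry. Keeping them in the denominator credits unobserved time as AE-free and lowers the AE rate. Dropping them, while keeping AEs from subjects who would have left later anyway, raises it. The same lead can therefore fall on either side of the 7.5% limit depending on which section is followed. With both rules in the plan, the choice could be made after the data are seen.

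**Working it through.** **Reproducing the plan's figures.** Exact binomial test, rejecting when P(X ≤ c | 7.5%) ≤ 0.025. At n = 750 the cut-off is c = 42, with error 0.0247 and power at a true AE rate of 5% of 80.1%. 750/0.9^5 = 1270.1 and 1000/0.9^5 = 1693.5, so 1271 and 1694 follow.

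**Inputs.** From the plan: N = 1694, attrition 10% per year, goals of 92.5% and 1%, exact two-sided 95% bounds. Assumed, because the plan does not give them: exits independent of AEs, and the timing of AEs (evenly spread over 5 years unless stated).

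**Reading A: Section 10.2 with all 1694 in the denominator.**

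Endpoint 1 passes with at most 105 events (upper bound 7.454%; 106 gives 7.518%). With complete follow-up, P(Bin(1694, 0.075) ≤ 105) = 2.1%, as intended.

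With yearly attrition d, the share of 5-year AEs that is observed is (1 − (1−d)^5) / (−5 ln(1−d)). For d = 10% this is 0.40951/0.52680 = 0.777. The expected crude rate at the null is 0.075 × 0.777 = 5.83%, below the 105/1694 = 6.20% cut-off.

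| Attrition per year | Share observed | Expected crude rate at true 7.5% | P(pass) |
|---|---|---|---|
| 2% | 0.951 | 7.13% | 7% |
| 5% | 0.882 | 6.62% | 26% |
| 10% | 0.777 | 5.83% | 76% |

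AE timing, at 10% attrition and a true 7.5%:
- Half of AEs in year 1: share 0.842, P(pass) 45%.
- Constant hazard: P(pass) 75%.
- Linearly increasing: share 0.709, P(pass) 95%.
- Extreme case, half of AEs at implant: P(pass) 24%.

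Truth further below the goal (10% attrition, even spread): 51% at 92.0% AE-free and 27% at 91.5%.

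Endpoint 2 passes with at most 8 events (8/1694 has upper bound 0.928%; 9/1694 has 1.006%). At a true 1%, P(Bin(1694, 0.01) ≤ 8) = 1.3% with complete follow-up. With a share of 0.777 it is 9% (5% to 15% over the half-in-year-1 and linearly increasing patterns).

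**Reading B: Section 2.4.3.** At a true AE rate of 5% and 10% attrition:
- Observed AEs: 0.05 × 0.777 = 0.0389 of those enrolled.
- AE-free completers: 0.95 × 0.59049 = 0.5610.
- Expected proportion: 0.0389/(0.0389 + 0.5610) = 6.5%, on about 1694 × 0.5998 = 1016 subjects.
- Simulated pass probability: about 22% (21% to 23% across runs and timing assumptions).

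At a true 7.5% the same formula gives 0.0583/(0.0583 + 0.5462) = 9.6%, and the lead almost never passes.

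**Kaplan-Meier at 5 years, same settings (simulation).** At a true 92.5%, the lower 95% bound exceeds 92.5% in 2.1% to 2.3% of runs with a log-log interval and 2.9% to 3.6% with a plain interval. At a true 95% it does so in about 95% to 97%.

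**The sponsor's own data.** The predecessor registry (Section 1.3.1) reports 29/1999 = 1.45% crude but 97.5% AE-free by Kaplan-Meier, that is 2.5%. Part of that gap is follow-up still running, but the direction is the same.

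**The case against.** **Section 2.4.3 is the more explicit rule.** It says who enters the final tests, and sizing on evaluable subjects makes sense only if exits leave the denominator. Section 10.2 is mainly about which adjudicated events count, and it says the same rules apply to Kaplan-Meier, which a crude denominator cannot. This stands. A reader might infer that the registry will pass a failing lead three times in four; the documents do not support that unconditionally. The figure needs Reading A, the attrition the plan calls a maximum, the assumed AE timing, and a lead at the goal. But the text does not rank the sections, and Section 2.4 supports Reading A.

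**Not everyone who exits is scored AE-free.** A counted AE before exit remains an event, and Section 10.3.1 counts deaths resulting from a lead-related AE. The dilution comes only from exits without a counted AE. Some of these are deaths, and a subject who died without an AE did not have one. The plan does not split the 10% by cause.

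**Endpoint 2.** It is tempting to contrast 8 permitted events on 1694 with 3 on 1000. That mostly reflects sample size: 8 is the correct exact cut-off for 1694 fully followed subjects. The relevant comparison is 9% against 1.3%. Section 2.3 also describes this endpoint as non-powered.

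**Safeguards exist.** Section 2.4.2 requires a report to FDA if observed survival falls below target or is projected to. In simulation, the 5-year Kaplan-Meier estimate is below 92.5% in about 49% of runs at a true 92.5%. The dilution would often be visible, but the formal test would still be passed.

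**Aligning 10.2 with 2.4.3 would suffice.** It removes the contradiction, but leaves a test that a lead at the expected 95% would usually fail.

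**Conclusion.** The contradiction is in the text, and at the planned attrition it can decide the result. Under Reading A the false-pass probability for endpoint 1 is 76% at 10% attrition per year with evenly spread AEs, and it exceeds 2.5% in every attrition and timing case examined at the null (7% at 2% attrition; 24% to 95% by timing at 10%). For endpoint 2 it is about 9%. Under Reading B the error is in the other direction, with about 22% power instead of 80% for a lead performing as expected. Both results assume 1694 subjects and exits independent of AEs. Which reading the sponsor intends cannot be settled from the documents, though 2.4.3 is the more specific. The conclusion does not depend on that choice, because neither denominator estimates the 5-year rate without bias.

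**What to change.** Use one rule in Sections 2.3, 2.4, 2.4.1, 2.4.3 and 10.2:

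- All ITT subjects contribute and are censored at exit, as Section 2.4.3 already defines for Kaplan-Meier. State explicitly how deaths unrelated to the lead are handled.
- Endpoint 1: compare the two-sided 95% lower bound of the 5-year Kaplan-Meier AE-free rate with 92.5%. Name the interval method; the log-log form held its error better here.
- Endpoint 2: compare the upper bound for each individual AE with 1%, using an interval method suited to rare events, named in advance.
- Restate the test basis in 2.3 and 2.4.1, which now specify the exact binomial test and exact intervals, and re-justify the sample size on that basis.
- In 10.2, delete the reference to total subjects or label the crude proportion as descriptive only.

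Cost: an amendment to wording and sample size justification, with no new data, since the Kaplan-Meier analysis and its censoring rule are already planned. Reported AE rates will be higher than the crude proportion, and the exact binomial test is given up.
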